4 ELIGIBILITY

- Subject population: Adolescents and young adults undergoing tonsillectomy
- Inclusion criteria
 - Adolescents and young adults aged 12-25 years will be eligible to be recruited if they undergo palatine tonsillectomy with or without adenoidectomy on the pediatric or general otolaryngology service of the University of Michigan Medical School, and if they are not:
 - Patients in foster care or patients with a legal guardian
 - Patients with developmental delays, such as autism
 - Patients who are non-English speaking
 - Patients with recent suicidal ideation
 - Patients undergoing emergent tonsillectomy

- Exclusion criteria for primary analysis analyzing prescribing
 - Patients who were approached for consent but declined
 - Patients with prescription opioid use prior to surgery
 - Patients undergoing additional major procedures at the same time as tonsillectomy
 - Patients enrolled in another study
 - Patients who are not prescribed opioids post-operatively
 - Patients who are enrolled in the “M-POP” pathway, which includes education about pain management and a small initial opioid prescription (10 doses)
 - Patients with hospitalization with length of stay > 1 day after surgery
- Additional exclusion criteria for secondary analysis examining patient-reported outcomes through surveys
 - Patients who were not reached for consent
 - Patients who do not complete the baseline and post-operative day 14 surveys
- Inclusion of vulnerable populations: The purpose of this study is to evaluate an intervention on opioid prescribing to adolescents and young adults. As such, minors must be included in the study.

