6 STUDY DESIGN AND PROCEDURES

- Study design
 - The study will use a difference-in-differences design in which changes before and after the intervention will be compared between a treatment group and a control group.
 - The treatment group will include all patients undergoing tonsillectomy at C.S. Mott Hospital by a pediatric otolaryngology faculty member at the University of Michigan.
 - The control group will include all patients undergoing tonsillectomy at University Hospital, Brighton Center for Specialty Care, or Livonia Center for Specialty Care by a general otolaryngology faculty member at the University of Michigan.
- Data collection procedures throughout the study
 - There will be three sets of surveys: a baseline survey, daily surveys on post-operative days 1-13, and a final survey on post-operative day 14. Post-operative surveys will be sent to all patients who enroll, including those who are not prescribed opioids post-operatively. These patients will not be included in the primary or secondary analysis but will be analyzed in a separate study examining pain recovery without opioids.
 - Baseline survey: Patients will be asked to complete a 10-15 minute survey assessing demographics, reason for tonsillectomy, current pain, chronic pain, history of opioid use, history of opioid misuse, family chronic opioid use, depression, substance use disorders, anxiety, sleep, and global health. Patients will be e-mailed a link to the baseline survey upon enrollment; for patients who cannot receive e-mail links, the survey will be administered over the phone. For patients at Mott or University Hospital recruited in-person, the baseline survey will be administered by a study team member in-person through Qualtrics on a tablet. Patients sent the baseline survey who do not complete it before surgery will be contacted via e-mail or by phone to remind them or approached in-person to complete it through Qualtrics on a tablet. If patients are contacted by phone, they will be given the option to complete the survey over the phone.

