- Daily surveys: At 12:01 am on post-operative days 1 through 13, patients will be e-mailed a daily link to complete a 1-minute online Qualtrics survey in which pain and opioid consumption over the prior 24 hours will be assessed. The post-operative day 7 survey will be similar except that it will include additional questions assessing pain over the prior 7 days. Patients who cannot receive e-mail links will not be sent daily surveys. E-mail or telephone follow-up will not occur for the daily surveys on post-operative days 1-13.
 - Final survey: on post-operative day 14, patients will be e-mailed a link to complete a 10-15-minute online Qualtrics survey assessing pain control, opioid use, opioid disposal, opioid misuse, acetaminophen/ibuprofen use, depression, anxiety, sleep, and health care utilization during the 14 days after surgery, including refills and visits to the emergency department or primary care for pain. Patients who cannot receive e-mail links will be called and the survey will be administered over the phone. Patients may be contacted via e-mail or by phone to remind them to complete surveys. If patients are contacted by phone, they will be given the option to complete the survey over the phone.
 - DataDirect and MiChart will be queried to determine opioid use prior to the day of surgery based on the admission history and physical, patient demographics, the dosing parameters of post-operative opioid prescriptions, the number of return visits for pain at the University of Michigan in the 14 days after surgery, and the number of opioid refills in the 14 days after surgery.
- Timeline
 - The pre-intervention period will start on October 1, 2019 and end September 30, 2020; the months of April and May 2020 will be excluded as elective surgeries were scaled down owing to the COVID-19 pandemic. The intervention will be implemented on October 1, 2020. The post-intervention period will start October 1, 2020 and end on July 31, 2021.
 - Nature of intervention
 - Currently, pediatric otolaryngology attendings and their residents use a MiChart tonsillectomy orderset with three options: patients < 12 years, patients ≥12 years, and M-POP. Under the orderset for patients ≥12 years, the default is currently 30 doses, consistent with the current departmental prescribing standard (see MiChart screenshot below).
 - During the pre-intervention period, no changes will be made to the default number of doses or any other dosing parameter.

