10 STATISTICAL CONSIDERATIONS

- Outcomes in primary analysis
 - Number of doses in the discharge opioid prescription
 - Proportion of patients in which the number of doses in the discharge opioid prescription equals the number of doses in the new default settings
 - Proportion of patients prescribed opioids at discharge
 - Proportion of patients prescribed opioids at discharge who had at least one opioid prescription refill from UM during the two weeks after surgery
 - Proportion of patients who saw a UM provider in an office due to pain during the two weeks after surgery

- Proportion of patients with at least one emergency department visit or hospitalization at UM for pain during the two weeks after surgery
- Additional outcomes in secondary analysis (based on data from the final post-operative day 14 survey)
 - Overall satisfaction with pain control during the two weeks after surgery (scale of 1-10)
 - Proportion of patients who reported that their pain was well-controlled
 - Proportion of patients whose overall pain control was rated as much worse or worse than expected
 - Proportion of patients whose pain has resolved by day 14 after surgery
 - Pain score over the past 7 days at its worst (scale of 0-10)
 - Pain score over the past 7 days on average (scale of 0-10)
 - Number of opioid doses taken during the two weeks after surgery
 - Proportion of patients with leftover doses of opioids
 - Proportion of patients with leftover doses who disposed of them
 - Proportion of patients who misused opioids belonging to others at least once during the two weeks after surgery
 - Proportion of patients who misused their own opioids at least once during the two weeks after surgery
 - PHQ-8 score (depression)
 - Score on PROMIS Pediatric Anxiety – Short Form 8a
 - Score on PROMIS Sleep Disturbance – Short Form 8a
 - Proportion of patients who saw their primary care provider (or a colleague) in the office due to poorly controlled pain at least once during the two weeks after surgery
 - Proportion of patients who visited an urgent care center due to poorly controlled pain at least once during the two weeks after surgery
 - Proportion of patients who visited a retail clinic due to poorly controlled pain at least once during the two weeks after surgery
 - Proportion of patients who went to an emergency department and/or were hospitalized due to poorly controlled pain at least once during the two weeks after surgery

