- Data from the daily surveys will be used to assess whether daily opioid consumption reports matches the consumption reported on the final post-operative day 14, and will also be analyzed in a separate study assessing the trajectory of pain and opioid use after tonsillectomy.
- We will fit linear or logistic regression models assessing outcomes as a function of an indicator of post-intervention status, an indicator of treatment group status, and its interaction, controlling for covariates such as demographics (e.g., age, sex) and baseline co-morbidities (e.g., depression, anxiety). We will graphically and statistically assess the comparability of pre-intervention monthly trends in outcomes between the treatment and control groups.

- We hypothesize that there will be no change in outcomes in the control group (i.e., that the post-intervention trend in outcomes in the control group will be an extension of the pre-intervention trend in outcomes). In contrast, we hypothesize that the number of doses and opioid consumption will drop in the treatment group after the intervention; that the proportion of patients with prescriptions concordant with the new defaults will increase after the intervention; and that there will be no change in balancing measures such as pain control or depression.
- Sensitivity analyses
 - Statistical modeling: we will explore whether results change when replacing the indicator of treatment group status with a vector of fixed effects for the prescribing clinician, and will explore the feasibility of using an interrupted time series approach instead of a difference-in-differences approach.
 - We will determine whether any otolaryngology residents wrote opioid prescriptions for both a pediatric otolaryngology and general otolaryngology patients in the post-intervention period, and exclude data from any such residents from the analysis
 - We will exclude opioid prescriptions written for patients of the chief of pediatric otolaryngology, who will be involved in setting the new defaults
- Subgroup analysis will occur by age group (ages 12-17 years vs 18 and older), gender, payer type (private/public), and baseline co-morbidities (e.g., depression and anxiety).
- We will separately analyze data from pediatric otolaryngology patients undergoing surgery outside of Mott and general otolaryngology patients undergoing surgery at Mott to assess for any spillover effects.

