- Sample size: Based on historical UM data, we estimate that there will be 113 patients in the treatment group and 85 in the control group for the primary analysis (total 198). If 65% consent to complete the surveys, then there will be 74 and 55 patients in the treatment and control groups for the secondary analysis, respectively (total 129).

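### Requiring both surveys for the secondary analysis discards observed day-14 outcomes, and no analysis of day-14 non-response is planned

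*Combined protocol and SAP*

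**What the plan says.** Among the additional exclusions for the secondary analysis, Section 4 lists "Patients who do not complete the baseline and post-operative day 14 surveys". Read literally this could mean patients who complete neither survey, but the natural reading is that both are required.

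Section 10 introduces the extra outcomes as "Additional outcomes in secondary analysis (based on data from the final post-operative day 14 survey". There are 18 of them, covering pain control, consumption, leftover doses and disposal, misuse, depression, anxiety, sleep and self-reported care-seeking. Section 6 sets no condition of baseline completion for receiving that survey: "Post-operative surveys will be sent to all patients who enroll, including those who are not prescribed opioids post-operatively". In Section 10 the baseline co-morbidities appear as model covariates and as subgroup factors.

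The plan expects some non-completion of both surveys. For baseline, "Patients sent the baseline survey who do not complete it before surgery will be contacted via e-mail or by phone"; for day 14, "Patients may be contacted via e-mail or by phone to remind them to complete surveys". The daily surveys on days 1-13 ask about pain and doses ("pain and opioid consumption over the prior 24 hours will be assessed"). Their stated uses are a separate study of recovery and a concordance check ("Data from the daily surveys will be used to assess whether daily opioid consumption reports matches the consumption reported on the final post-operative day 14").

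The sample-size paragraph reaches the secondary-analysis numbers from consent alone: "If 65% consent to complete the surveys", there will be 74 and 55 patients. The sensitivity analyses in Section 10 cover clinician fixed effects, interrupted time series, residents who cross services and the chief's patients. None concerns non-response. Section 9 has a monthly check of missingness patterns, which is quality control and not an analysis method.

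**The concern.** Two separate problems follow from this one line.

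The first is waste. A patient who answers the day-14 survey but never completed the baseline survey has every secondary outcome recorded and lacks only some covariates. Demographics are also drawn from the medical record (Section 6), so often only the baseline co-morbidities would be missing. Removing that patient costs precision and representativeness in an already small set.

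The second is selection. The day-14 survey is answered after the prescription that the intervention is meant to change. Whether a patient answers may depend on pain or on how many doses were supplied. If that dependence changes in the treated group after the default is lowered, a difference-in-differences among responders is no longer a clean comparison. The outcomes exposed to this include pain control, depression and misuse, which Section 3 names as possible risks. Section 10 expects no change in balancing measures, and the plan has no analysis to show how far such a result depends on who replied. This applies only to the day-14 condition, because the baseline survey is meant to be completed before surgery.

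**Working it through.** **Stated inputs (Section 10).** 113 treatment and 85 control patients (198 in total); 65% consent; 74 and 55 (129) in the secondary analysis.

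**Reproducing the plan's figure.**
- 113 × 0.65 = 73.45 (stated 74)
- 85 × 0.65 = 55.25 (stated 55)
- 198 × 0.65 = 128.7 (stated 129)

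The figure of 129 is therefore the number consenting. It equals the analysed number only if every consenter completes both surveys.

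**Observed outcomes discarded.** No completion rates are given, so I assume day-14 completion d = 70-90% and baseline completion among day-14 responders b = 80-95%. The number with an observed outcome is 129 × d, the number kept by the rule is 129 × d × b, and the number discarded is 129 × d × (1 − b).

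| d | b | Day-14 responders | Kept by rule | Discarded |
|---|---|---|---|---|
| 0.70 | 0.95 | 90.3 | 85.8 | 4.5 |
| 0.70 | 0.80 | 90.3 | 72.2 | 18.1 |
| 0.80 | 0.90 | 103.2 | 92.9 | 10.3 |
| 0.90 | 0.95 | 116.1 | 110.3 | 5.8 |
| 0.90 | 0.80 | 116.1 | 92.9 | 23.2 |

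The range is about 5 to 23, with about 10 in the central case.

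**Precision.** Assume two-sided alpha 0.05, 80% power, independent patients, no covariate gain, and an equal split of each group between periods. Section 6 gives 10 usable months before the change (12 less April and May 2020) and 10 after. The minimum detectable effect in SD units is (1.960 + 0.842) × √(4/nT + 4/nC).
- All 129 consenters (74, 55): 2.802 × 0.356 = 1.00
- Day-14 responders at d = 0.80 (59.2, 44.0): 1.00/√0.80 = 1.12
- Both surveys at d = 0.80, b = 0.90 (53.3, 39.6): 1.00/√0.72 = 1.18

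**Selection, illustration only.** Suppose 70% of patients truly have well-controlled pain in all four group-by-period cells, and response depends on pain control only in the treated post-intervention cell. The proportion seen there is 0.7 × rw / (0.7 × rw + 0.3 × rp), where rw and rp are the response rates of well and poorly controlled patients.
- rw = 0.85, rp = 0.70: 0.595/0.805 = 73.9%, a spurious +3.9 points
- rw = 0.85, rp = 0.60: 0.595/0.775 = 76.8%, a spurious +6.8 points
- rw = 0.70, rp = 0.85: 0.490/0.745 = 65.8%, a spurious −4.2 points

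The sign depends on which patients reply less often, and the documents do not say.

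**The case against.** The plan works to limit the loss. Baseline can be completed by e-mail link, phone or tablet, with reminders. The final survey carries a $10 payment, reminders and a phone option. If these succeed, few patients are discarded. The precision gain in the central case is also modest, 1.12 against 1.18 SD.

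The selection examples are small beside random error. For a 70% outcome with all 129 consenters, the standard error of the difference-in-differences is about √(0.7 × 0.3) × 0.356 = 0.163, or 16 points. They also put the differential response in a single cell, whereas a pattern shared by all four cells would largely cancel.

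These points stand as limits on size. They do not defend the rule, which gains nothing by dropping an observed outcome for want of covariates, and they do not replace a non-response analysis.

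A reader might infer more than the documents support:
- **That the data recorded on excluded patients go unused.** The rule applies only to the secondary analysis. Record-based refills, office visits, and emergency visits or hospitalizations for pain are primary-analysis outcomes, and these patients remain there.
- **That everyone without both surveys is usable data lost.** A patient with no day-14 survey has no observed secondary outcome. Only day-14 responders without a baseline survey count as discarded outcomes.
- **That daily reports would fill the gap.** They are not sent to patients who cannot receive e-mail links and get no follow-up, so day-14 non-responders may lack them too.

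**Conclusion.** The point holds as a fault in the secondary analysis set and a gap in its handling of non-response. The rule discards about 5 to 23 observed outcome records out of 129, about 10 in the central case, under completion rates that are my assumptions. The cost in precision is small but avoidable.

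The selection problem is real in kind, but the documents fix neither its size nor its direction. It is tempting to conclude that the rule biases the balancing measures toward the hypothesised absence of change and so hides harm. The documents do not support that. Under no true effect, lower response among poorly controlled treated patients gives an apparent benefit and the opposite pattern an apparent harm. Bias toward no change would need a true harm together with a particular response pattern, and nothing in the plan establishes either. The primary prescribing and record-based utilization analysis is not affected.

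**What to change.** Reword the Section 4 exclusion so that it removes only patients without a day-14 survey. Every otherwise eligible consenter with a day-14 outcome is then analysed, and the ambiguity between both and neither disappears. In Section 10:

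- Impute missing baseline covariates, using the record-based demographics.
- Report completion of each survey by group and period.
- Add one sensitivity analysis for day-14 non-response: inverse-probability weighting, or multiple imputation from record, baseline and available daily-survey data.
- Keep patients who completed both surveys as a further sensitivity analysis.

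Imputing missing day-14 outcomes should not become the main analysis. With 18 outcomes, and cells of about 37 (74/2) and 28 (55/2) patients before any loss, imputation within group and period would probably be unstable for the rarer binary outcomes.

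The cost is a wording change and modest analysis work, with no new data. The methods assume missingness at random given the observed data, so they would not remove bias if response depends on day-14 pain that those data do not capture. The daily surveys carry no information on depression, anxiety, sleep or misuse, so for those outcomes the sensitivity analysis rests mainly on baseline and record data.

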5 SUBJECT ENROLLMENT

- Screening
 - Patients scheduled to undergo tonsillectomy during the study period will be identified using the surgical scheduling system and screened to against age criteria.
- Enrollment
 - The study team will recruit all eligible patients. Recruitment will occur over the phone or in-person during the 14-day period before the day of surgery for patients undergoing tonsillectomy at C.S. Mott Hospital or University Hospital. A study team member will e-mail patients who enroll with a PDF version of the consent and a pain journal they can print to record the number of opioid doses consumed. For those patients who cannot be contacted, in-patient recruitment will occur pre-operatively on the day of surgery. A study team member will provide patients who enroll with a paper pain journal they can use to record the number of opioid doses consumed.
 - Recruitment will occur over the phone during the 14-day period before the day of surgery for patients undergoing tonsillectomy at the Brighton Center for Specialty Care or Livonia Center for Specialty Care. A study team member will e-mail patients who enroll with a PDF version of the

consent and a pain journal they can print to record the number of opioid doses consumed.

- Incentives
 - Subjects will be compensated \$10 for completing the baseline survey, \$10 for completing all 13 daily post-operative surveys, and \$10 for completing the final survey on post-operative day 14. Subjects will be compensated based on the number of sets of surveys completed (e.g., if they complete the baseline and post-operative surveys, they will receive \$20). Compensation will be mailed after post-operative day 14.

6 STUDY DESIGN AND PROCEDURES

- Study design
 - The study will use a difference-in-differences design in which changes before and after the intervention will be compared between a treatment group and a control group.
 - The treatment group will include all patients undergoing tonsillectomy at C.S. Mott Hospital by a pediatric otolaryngology faculty member at the University of Michigan.
 - The control group will include all patients undergoing tonsillectomy at University Hospital, Brighton Center for Specialty Care, or Livonia Center for Specialty Care by a general otolaryngology faculty member at the University of Michigan.
- Data collection procedures throughout the study
 - There will be three sets of surveys: a baseline survey, daily surveys on post-operative days 1-13, and a final survey on post-operative day 14. Post-operative surveys will be sent to all patients who enroll, including those who are not prescribed opioids post-operatively. These patients will not be included in the primary or secondary analysis but will be analyzed in a separate study examining pain recovery without opioids.
 - Baseline survey: Patients will be asked to complete a 10-15 minute survey assessing demographics, reason for tonsillectomy, current pain, chronic pain, history of opioid use, history of opioid misuse, family chronic opioid use, depression, substance use disorders, anxiety, sleep, and global health. Patients will be e-mailed a link to the baseline survey upon enrollment; for patients who cannot receive e-mail links, the survey will be administered over the phone. For patients at Mott or University Hospital recruited in-person, the baseline survey will be administered by a study team member in-person through Qualtrics on a tablet. Patients sent the baseline survey who do not complete it before surgery will be contacted via e-mail or by phone to remind them or approached in-person to complete it through Qualtrics on a tablet. If patients are contacted by phone, they will be given the option to complete the survey over the phone.

- Daily surveys: At 12:01 am on post-operative days 1 through 13, patients will be e-mailed a daily link to complete a 1-minute online Qualtrics survey in which pain and opioid consumption over the prior 24 hours will be assessed. The post-operative day 7 survey will be similar except that it will include additional questions assessing pain over the prior 7 days. Patients who cannot receive e-mail links will not be sent daily surveys. E-mail or telephone follow-up will not occur for the daily surveys on post-operative days 1-13.
 - Final survey: on post-operative day 14, patients will be e-mailed a link to complete a 10-15-minute online Qualtrics survey assessing pain control, opioid use, opioid disposal, opioid misuse, acetaminophen/ibuprofen use, depression, anxiety, sleep, and health care utilization during the 14 days after surgery, including refills and visits to the emergency department or primary care for pain. Patients who cannot receive e-mail links will be called and the survey will be administered over the phone. Patients may be contacted via e-mail or by phone to remind them to complete surveys. If patients are contacted by phone, they will be given the option to complete the survey over the phone.
 - DataDirect and MiChart will be queried to determine opioid use prior to the day of surgery based on the admission history and physical, patient demographics, the dosing parameters of post-operative opioid prescriptions, the number of return visits for pain at the University of Michigan in the 14 days after surgery, and the number of opioid refills in the 14 days after surgery.
- Timeline
 - The pre-intervention period will start on October 1, 2019 and end September 30, 2020; the months of April and May 2020 will be excluded as elective surgeries were scaled down owing to the COVID-19 pandemic. The intervention will be implemented on October 1, 2020. The post-intervention period will start October 1, 2020 and end on July 31, 2021.
 - Nature of intervention
 - Currently, pediatric otolaryngology attendings and their residents use a MiChart tonsillectomy orderset with three options: patients < 12 years, patients ≥12 years, and M-POP. Under the orderset for patients ≥12 years, the default is currently 30 doses, consistent with the current departmental prescribing standard (see MiChart screenshot below).
 - During the pre-intervention period, no changes will be made to the default number of doses or any other dosing parameter.
 - During the month of September 2020, opioid consumption data will be reviewed by the chief of pediatric otolaryngology. A new default

- number of doses lower than 30 will be chosen based on the level and distribution of opioid consumption.
- On October 1, 2020, the tonsillectomy orderset will be changed. The new orderset will have three options for patients ≥ 12 years: one for oxycodone solution among patients < 50 kg, one for oxycodone solution among patients ≥ 50 kg, and one for oxycodone tablets. Each of these options will auto-populate the default doses field using the new setting.
 - The new orderset will display for patients at C.S. Mott Hospital only. Thus, all patients in the treatment group (patients undergoing tonsillectomy at Mott by pediatric otolaryngology attendings) will have clinicians who are exposed to the new default settings. The tonsillectomy orderset will not be changed at University Hospital, Brighton, or Livonia. Thus, all patients in the control group (patients undergoing tonsillectomy in these locations by general otolaryngology attendings) will have clinicians who will not be exposed to the new default settings, even if they use the pediatric otolaryngology tonsillectomy orderset.

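### Three control sites share one group indicator, so a change in their mix between periods could move the effect estimate; site indicators would remove this cheaply

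*Combined protocol and SAP*

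**What the plan says.** Section 6 (Study design) sets one site against three. "The treatment group will include all patients undergoing tonsillectomy at C.S. Mott Hospital by a pediatric otolaryngology faculty member", whereas "The control group will include all patients undergoing tonsillectomy at University Hospital, Brighton Center for Specialty Care, or Livonia Center for Specialty Care", in the control case under general otolaryngology faculty.

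Section 10 models each outcome by linear or logistic regression on "an indicator of post-intervention status, an indicator of treatment group status, and its interaction". Adjustment is then described as follows: "controlling for covariates such as demographics (e.g., age, sex) and baseline co-morbidities (e.g., depression, anxiety". The covariate list is given by example, so site is neither named nor ruled out. No table of control-site mix by period is planned.

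Two planned checks bear on the point. One is a sensitivity analysis "replacing the indicator of treatment group status with a vector of fixed effects for the prescribing clinician". The other concerns trends: "We will graphically and statistically assess the comparability of pre-intervention monthly trends in outcomes between the treatment and control groups".

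On timing, section 6 runs the pre-period from October 2019 to September 2020, where "the months of April and May 2020 will be excluded as elective surgeries were scaled down owing to the COVID-19 pandemic". The post-period runs from October 2020 to July 2021. Each therefore keeps ten months, but not the same ten: August and September appear only before the change, April and May only after it.

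**The concern.** With one indicator for the whole control group, the control pre-post change is a difference between two pooled means. If University Hospital and the two specialty centers have different outcome levels, and the pool draws on them in different proportions before and after October 2020, part of that change is composition. It is then subtracted from the change at Mott. Mott is one site and has no site mix of its own to offset it.

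The error can go either way. A control mix that moves toward lower-prescribing sites hides a true reduction at Mott; one that moves toward higher-prescribing sites exaggerates it. The pre-trend check uses pre-intervention months only, so it cannot see a change in mix between the periods.

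**Working it through.** **Inputs from the documents.** Section 10: 113 treatment and 85 control patients for the primary analysis. Section 6: one treatment site, three control sites, two periods of ten retained months.

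**Assumed inputs, not in the documents.** An even split of patients across periods (56.5 and 42.5 per cell); outcome SD of 6, 8 or 10 doses; gap D between University Hospital and the centers of 2, 5 or 10 doses; fall s in University Hospital's share of controls of 0.1, 0.2 or 0.3.

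**1. The plan's own figures.** 113 + 85 = 198. At 65% consent, 0.65 × 113 = 73.45 (stated as 74) and 0.65 × 85 = 55.25 (stated as 55), total 129. These reproduce. No SD, effect size or power is stated, and nothing is split by site or period.

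**2. Bias.** Let p0 and p1 be University Hospital's share of controls before and after, and s = p0 − p1. Mix alone changes the control mean by (p1 − p0) × D = −sD. The interaction is the treated change minus the control change, so its bias is +sD. It is zero if D = 0 or s = 0.

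- Smallest assumed case: 0.1 × 2 = 0.2 doses.
- Middle case: 0.2 × 5 = 1.0 dose.
- Largest case: 0.3 × 10 = 3.0 doses.

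**3. Standard error.** SE = SD × √(2/56.5 + 2/42.5) = 0.287 × SD, which gives 1.7, 2.3 and 2.9 doses at SD 6, 8 and 10.

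**4. Effect on a nominal 5% test.** With b = sD, the rejection rate when there is no true effect is Φ(−1.96 + b/SE) + Φ(−1.96 − b/SE). At SD 8:

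| D (doses) | s | Bias (doses) | Bias / SE | False-positive rate |
|---|---|---|---|---|
| 2 | 0.1 | 0.2 | 0.1 | 5.1% |
| 5 | 0.2 | 1.0 | 0.4 | 7.2% |
| 5 | 0.3 | 1.5 | 0.7 | 10.0% |
| 10 | 0.3 | 3.0 | 1.3 | 25.7% |

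**5. Which models remove it.** Simulation, 8,000 runs per setting: true effect 0, D = 5, University Hospital share 65% before and 35% after, SD 8. Entries are the mean interaction estimate in doses (Monte Carlo error about 0.03), with its empirical SE in parentheses.

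| Model | Prescribers stay at one control site | Prescribers work across control sites |
|---|---|---|
| Group indicator (as planned) | 1.54 (2.381) | 1.48 (2.350) |
| Site indicators | 0.03 (2.411) | −0.04 (2.380) |
| Clinician fixed effects | 0.04 (2.479) | 1.48 (2.410) |

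**6. Price of site indicators in the linear model.** Here 2.411/2.381 = 1.013, about 1%. With a stable mix split 50/25/25 the average ratio was 1.006. With the 30-point shift but no site gap, when the adjustment was not needed, it was 2.411/2.327 = 1.036.

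**7. Chance movement in the mix.** With about 42 controls per period and a 50% share, the SE of a share change is √(2 × 0.25/42) = 0.109, or about 11 points.

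**8. Rare binary outcomes.** At an assumed 25% share, a center has 0.25 × 85 ≈ 21 controls. At an assumed 3% event rate, the chance that it has no events is 0.97^21 = 0.53. With about 14 survey controls (0.25 × 55) it is 0.97^14 = 0.65. A logistic site term is not estimable for a center with no events.

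**The case against.** The strongest reply is that both factors in the product are assumed. No site gap is documented. All control patients belong to one service, and section 6 refers to a departmental standard of 30 doses, which gives no support to a gap as large as 10. The covariates may absorb part of any case-mix difference. A shift near 10 points is ordinary chance variation (step 7), which the pooled model's standard error already reflects on average. This all stands, and it limits the point to a conditional one.

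A reader might also infer that the recruitment and exclusion rules themselves create a shift. Section 5 says "Recruitment will occur over the phone during the 14-day period before the day of surgery for patients undergoing tonsillectomy at the Brighton Center", and Livonia has the same phone-only rule, while University Hospital adds in-person approach. The exclusions for refusing consent and for longer stays may also fall unevenly on a hospital and two centers. But these rules are the same in both periods. A constant imbalance does not bias a difference-in-differences estimate; it would matter only if its effect changed over time, and nothing in the documents says that it did. Recruitment route also reaches the primary analysis only through patients who decline, because those never reached are excluded only from the survey analysis.

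The clinician fixed effects are a real partial safeguard. For prescribing outcomes, one can argue that a site gap mostly means different clinicians. Still, the analysis is exploratory and does not replace the main estimate, and step 5 shows that it leaves the bias untouched if prescribers cross control sites and levels differ by location. The documents do not say whether they cross. Section 10 does allow that some residents may prescribe for both services, so one prescriber per site cannot be taken for granted.

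**Conclusion.** The point holds in conditional form: a change in control-site mix between periods, combined with a difference in site levels after adjustment, enters the interaction one for one. Over the assumed ranges this is 0.2 to 3.0 doses, against a standard error of 1.7 to 2.9 doses. At SD 8 the false-positive rate stays near 5% in the mildest case and reaches 25.7% only when the largest gap and the largest shift coincide. D, s, SD, the even period split and the clinician layout are all assumptions.

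The cutback in elective surgery within the pre-period and the unmatched calendar months make a shift plausible, but the documents do not show one. A reader might go further and conclude that the pooled comparison is valid only if the three sites contribute in constant proportions, or that the estimate is already biased. Neither follows: with equal site levels after adjustment the mix does not matter, and no site-level data are given. This is a cheap improvement to the analysis, not a defect that undermines the design.

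**What to change.** - **Continuous outcomes, starting with number of doses.** In the main linear model, replace the treatment-group indicator with indicators for Mott, University Hospital, Brighton and Livonia. Keep the post indicator and the post × treatment interaction. Each site lies wholly in one group, so the site terms absorb the group indicator and the interaction stays identified.
- **Binary outcomes.** Use site indicators where event counts allow. For rare outcomes (refills, emergency visits, misuse), prespecify either a linear probability or penalized logistic model with site terms, or keep the group indicator and report the site-adjusted result as a sensitivity analysis.
- **Reporting.** Tabulate patient counts by site and period.

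The cost is SAP wording and two degrees of freedom. The standard error in the linear model rises by about 1% (0.6% to 3.6% across the settings in steps 5 and 6), and site terms may be sparse for rare outcomes. No new data are needed, because surgical location is already required to assign the groups.
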